10.6.2.1 HELLP Syndrome

Haemolysis, Elevated Liver enzymes, and Low Platelets

10.6.2.2 Eclampsia

The occurrence of one or more seizures in a woman with pre-eclampsia

10.6.3 Chronic hypertension with superimposed pre-eclampsia

Characterized by;

- New-onset proteinuria (≥300 mg/24 h) in a woman with hypertension but no proteinuria before 20 weeks' gestation and,
- A sudden increase in proteinuria or BP, or a platelet count of less than 100,000/mm³, in a woman with hypertension and proteinuria before 20 weeks' gestation [15].

10.6.4 Additional Primary Outcomes

- Adverse maternal outcomes
- Adverse perinatal outcomes
- Mode of delivery

10.7 End Points (Secondary Outcomes); Conclusion of Pregnancy

Data on the following secondary study outcomes will be collected.

10.7.1 SGA

Neonates whose birth weight is less than the 10th percentile for that particular gestational age or two standard deviations below the population norms on the growth charts. The definition considers only the birth weight without any consideration of the in-utero growth and physical characteristics at birth.

10.7.2 Gestational Diabetes

Any degree of glucose intolerance with onset or first recognition during pregnancy. Developed during the second and third trimester of pregnancy, characterized by a marked insulin resistance secondary to placental hormonal release.

10.7.3 Sampling Adherence

Data relating to the following will be collected and analysed;

- Frequency of missed samples
- Dropout rate
- 'Dry' samples received

10.7.4 Definition of HDP

Blood Pressure

- Systolic blood pressure ≥130 mm Hg on 1 or more occasions
- Diastolic blood pressure ≥80 mm Hg on 1 or more occasions

Urine

- Urine protein dipstick test 1+ or more
- Urinary protein/creatinine ratio ≥0.30 mg/mg
- Urinary protein ≥300 mg per day in timed collection

Bloods

- New-onset low platelet count ≤100,000 x 109/L
- New onset elevated serum creatinine ≥1.0 mg/dL
- New-onset transaminase elevation above limits of normal for local laboratory

Symptoms

- New-onset headache unresponsive to medication and not accounted for by alternative diagnoses
- New-onset visual symptoms

Fetus

- Fetal growth restriction with AC/estimated fetal weight ≤10th percentile

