3 SALURATE STUDY SUMMARY

| Study Title | Validation of salivary uric acid remote self-monitoring for early prediction of | | | | |
|------------------------|---|--|--|--|--|
| | hypertensive disorders of pregnancy. | | | | |
| Short Title | The Salurate Study. | | | | |
| Objective | To clinically and logistically validate a novel remote self-monitoring screening system | | | | |
| | that uses the measurement of salivary uric acid to identify women who are at risk of | | | | |
| | developing hypertensive disorders of pregnancy (HDP) several weeks earlier than | | | | |
| | current methods. | | | | |
| Study design | A multi-center observational, analytical cohort study conducted over a period of 18 | | | | |
| | months with health economics evaluation. | | | | |
| | | | | | |
| | The Salurate Study is non-interventional; data collected will not result in any changes | | | | |
| | to the participants' care pathway. | | | | |
| Study | St. George's University Hospitals NHS Foundation Trust | | | | |
| Centres | Epsom and St. Helier University Hospitals NHS Trust | | | | |
| Sample size | n=4000 pregnant women | | | | |
| Eligibility | Inclusion criteria: Pregnant women from age 16, with a viable singleton pregnancy at | | | | |
| criteria (overview) | >12 weeks' gestation and able to provide informed consent. Full list section 8.1. | | | | |
| (overview) | | | | | |
| | Exclusion criteria: Physical incapacity, lack of access to a smartphone and/or the | | | | |
| | internet data at home, language or educational barriers that would cause an inability | | | | |
| • | to read the instructions for use (IFU) or use the App. Full list section 8.2. | | | | |
| Outcome | Primary Outcome: | | | | |
| ivieasules | a) Clinical diagnosis of HDP to include; gestational hypertension, pre-eclampsia, | | | | |
| | and chronic hypertension with superimposed pre-eclampsia | | | | |
| | Secondary outcomes: | | | | |
| | b) To assess whether Salurate could detect other important placentally- | | | | |
| | mediated adverse outcomes for the woman and baby including but not | | | | |
| | limited to fetal growth restriction (FGR) and gestational diabetes (GDM). | | | | |
| | c) To assess the cost effectiveness of routine Salurate testing compared to | | | | |
| | current care methods. | | | | |
| | d) To assess the degree of compliance of pregnant women to a self-sampling | | | | |
| | weekly test regimen. | | | | |

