10.6 End Points (Primary Outcomes); Conclusion of Pregnancy

Clinical diagnoses of the following outcomes will be collected and recorded on the participant's CRF for a period of **6** weeks following the conclusion of pregnancy. Definitions 10.6.1 to 10.6.3.2 based on NICE Clinical Knowledge Summaries. The Salurate study's primary outcome is to predict HDP, the primary conditions of which are defined below.

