10.6.1 Gestational hypertension

New hypertension presenting after 20 weeks, without significant proteinuria

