10.6.2 Pre-eclampsia

New onset hypertension presenting after 20 weeks, *and* the coexistence of 1 or more of the following new-onset conditions.

New onset of hypertension (over 140 mmHg systolic or over 90 mmHg diastolic) after 20 weeks of pregnancy and the coexistence of 1 or more of the following new-onset conditions:

- Proteinuria
- Other maternal organ dysfunction:
 - $\circ~$ Renal insufficiency (creatinine 90 micromol/litre or more, 1.02 mg/100 ml or more).
 - Liver involvement (elevated transaminases [alanine aminotransferase or aspartate aminotransferase over 40 IU/litre] with or without right upper quadrant or epigastric abdominal pain).
 - Neurological complications such as eclampsia, altered mental status, blindness, stroke, clonus, severe headaches or persistent visual scotomata.
 - Haematological complications such as thrombocytopenia (platelet count below 150,000/microlitre), disseminated intravascular coagulation or haemolysis
 - Uteroplacental dysfunction such as fetal growth restriction, abnormal umbilical artery doppler waveform analysis, or stillbirth.

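### Section 10.7.4, headed as the definition of HDP, conflicts with the primary-outcome definitions in section 10.6, so the reference standard for the accuracy analysis is ambiguous

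*Protocol*

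**What the plan says.** The study summary (section 3) gives the primary outcome as "Clinical diagnosis of HDP to include; gestational hypertension, pre-eclampsia", with chronic hypertension with superimposed pre-eclampsia as the third condition. Section 10.6 states: "The Salurate study's primary outcome is to predict HDP, the primary conditions of which are defined below". Three definitions follow:

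- 10.6.1, gestational hypertension: "New hypertension presenting after 20 weeks, without significant proteinuria". No blood pressure figure is given.
- 10.6.2, pre-eclampsia: "New onset of hypertension (over 140 mmHg systolic or over 90 mmHg diastolic) after 20 weeks of pregnancy", together with at least one further new-onset condition.
- 10.6.3, chronic hypertension with superimposed pre-eclampsia: two criteria of its own, based on proteinuria, blood pressure and platelets.

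Section 10.7.4 is placed among the secondary outcomes, but its heading presents it as the definition of HDP. Its first item is "Systolic blood pressure ≥130 mm Hg on 1 or more occasions"; the next is the same for diastolic pressure at 80 or more. Lists of urine, blood, symptom and fetal items follow.

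Section 15 splits the cohort by HDP present or absent. It reports sensitivity, specificity, PPV and NPV for the primary outcome, and compares how early Salurate and traditional methods indicate it.

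**The concern.** In a diagnostic-accuracy study the case definition is the reference standard. Every headline result, including lead time, depends on who counts as a case and from what date. Here a subsection that carries the outcome's own name uses lower blood pressure cut-offs than the only ones stated in 10.6 for new hypertension. It drops the 20-week condition and does not require the raised pressure to be new. It also includes fetal growth restriction, which the protocol elsewhere treats as a secondary outcome.

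This is a conflict between stated passages, not detail left to an analysis plan. Section 12 says that the case report form records the HDP endpoints as the protocol defines them, so whoever abstracts the records at the two sites works from these passages. Section 12 also has the register linking identities to study IDs destroyed on completion, so re-abstracting through that link would not be possible afterwards.

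**Working it through.** **1. The plan's own figures.** Section 15 gives 4,000 women, 11.5% with any event and 2.5% with IUGR.
- Events: 4,000 × 0.115 = 460; 4,000 × 0.025 = 100. Both agree.
- 95% half-width = 1.96 × √(s(1 − s)/n). For n = 460: 4.57 points at s = 0.5 and 2.74 at s = 0.9 (stated 5 and 3). For n = 100: 9.80 and 5.88 (stated 10 and 6). These agree after rounding.

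The arithmetic is sound. However, the 11.5% covers pre-eclampsia, pregnancy-induced hypertension and IUGR together, so it is tied to neither HDP definition and cannot settle which applies.

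**2. The sections side by side.**

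| | 10.6.1 | 10.6.2 | 10.7.4 |
|---|---|---|---|
| Blood pressure | not stated | above 140 or above 90 | 130 or more; 80 or more |
| Number of readings | not stated | not stated | one suffices |
| After 20 weeks | yes | yes | not stated |
| Blood pressure must be new | yes | yes | not stated |
| Combination rule | no significant proteinuria | at least one further condition | none |

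**3. Test cases.** Assume no hypertension before 20 weeks in (a) to (c).

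(a) 134/82 at 30 weeks with new proteinuria above 300 mg per day. She meets both blood pressure items and a urine item of 10.7.4. She is not pre-eclampsia under 10.6.2, because 134 is not above 140 and 82 is not above 90. If the proteinuria counts as significant, 10.6.1 excludes her as well. The conflict stands whether 10.7.4 needs any one item or blood pressure plus another item.

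(b) Exactly 140/90 at 30 weeks with the same proteinuria. She meets the items of 10.7.4 but fails 10.6.2, which asks for values above those limits.

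(c) 145/92 at 30 weeks with proteinuria only. She is a case under 10.6.2. She also meets 10.7.4 on an any-item or blood-pressure-plus-one reading, but not if all five groups in 10.7.4 were required.

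(d) 132/82 once at 14 weeks, nothing else. She meets the blood pressure items of 10.7.4 but fails the 20-week condition of 10.6.1 and 10.6.2. She is a case under 10.7.4 only if a blood pressure item alone is enough.

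By (a) and (c), the two sections disagree about some women under each of these combination rules.

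**4. What a mixed definition does.** Let a fraction c be cases under the narrower rule, flagged with probability s. Let the wider rule raise prevalence to p, with the added women flagged with probability f. Apparent sensitivity is [c·s + (p − c)·f]/p. All inputs here are assumptions: c = 0.115, s = 0.90, f = 0.10.
- p = 0.15: (0.1035 + 0.0035)/0.15 = 0.71
- p = 0.20: (0.1035 + 0.0085)/0.20 = 0.56
- p = 0.30: (0.1035 + 0.0185)/0.30 = 0.41

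If f were also 0.90, sensitivity would not change. This shows the mechanism only; the document supplies neither p nor f.

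**5. Two drafting slips in the same sections.**
- In 10.6.3 the first criterion applies "in a woman with hypertension but no proteinuria before 20 weeks' gestation and" is followed by a criterion for women who had proteinuria before 20 weeks. These are mutually exclusive presentations.
- 10.7.4 prints "New-onset low platelet count ≤100,000 x 109/L". With the superscript restored this is 100,000 × 10⁹/L. The 100,000/mm³ in 10.6.3 equals 100 × 10⁹/L, so the printed limit is 1,000 times higher. A lost superscript does not explain that factor.

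**The case against.** The strongest reply is that the protocol already names its governing section. Section 10.6 says it defines the primary conditions, the summary lists the same three, and 10.7.4 is filed under secondary outcomes. The endpoint is also a recorded clinical diagnosis, so nobody is told to search the notes for a single reading of 130/80. Section 13.2 adds a monthly independent check of 10% of case report forms, and form HR-P-55, which is not shown, may already carry one definition.

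Much of this stands. It means 10.7.4 is better seen as a stray, conflicting subsection than as a second co-equal primary definition, and a reader who inferred that the primary result would be uninterpretable would go too far. It does not remove the conflict. The heading of 10.7.4 claims the outcome's name, nothing says that it is subordinate, and a spot-check of abstraction cannot show which definition was meant.

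Other strong readings also fail:

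- A reader might apply the 140/90 limits and the additional condition to all HDP. They belong to pre-eclampsia only.
- A reader might count every woman with one reading of 130/80 as a case and set the total against 460 events. The document gives no blood pressure distribution and does not say that one item suffices, and the 460 include IUGR.
- A reader might say that any platelet count meets the 10.7.4 limit. The item requires a new-onset low count. Nor is "platelet count below 150,000/microlitre" in 10.6.2 in itself a contradiction of the limit in 10.6.3, since the two concern different conditions.
- A reader might conclude that superimposed pre-eclampsia can never be recorded. That is too literal for a clinical diagnosis, and each criterion carries its own qualifier.
- The creatinine limits (1.02 mg/100 ml and 1.0 mg/dL) hardly differ and need no separate point.

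**Conclusion.** The concern holds as an internal contradiction in the reference standard. Sections 10.6 and 10.7.4 can classify the same woman differently, as test case (a) shows from the stated thresholds without any assumed blood pressure distribution. That 10.7.4 applies at any gestation is an inference from its silence, and case (d) depends on it; case (a) does not.

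The consequence is ambiguity in who counts as a case for sensitivity, specificity, PPV, NPV and lead time. Its size cannot be computed from the document, because no prevalence is given under either rule and HR-P-55 is not available. The sample-size arithmetic is unaffected. The conflict should be resolved before outcomes are abstracted. No view is taken here on which threshold is clinically right.

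**What to change.** Reconcile sections 10.6 to 10.6.3 with 10.7.4 in one amendment:

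1. Name one governing definition of HDP for the primary analysis. Section 10.6 is the one the protocol points to.
2. Delete 10.7.4, or relabel it as a secondary or sensitivity definition with an explicit rule for combining its items.
3. State the blood pressure threshold that applies to gestational hypertension in 10.6.1.
4. Make case report form HR-P-55 carry the governing definition.
5. In the same edit, correct the connector in 10.6.3 and, if 10.7.4 is kept, its platelet unit.

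The choice of clinical thresholds stays with the sponsor. The cost is protocol wording and a check of the form; no extra participants or procedures are needed.

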11 ADVERSE EVENT REPORTING

11.1 Safety Reporting

11.1.1 Adverse Event Definitions

Adverse EventAn event in which care resulted in an undesirable clinical outcome – an outcome not(AE)caused by underlying disease – that prolonged hospital care, caused permanent

| | harm or requires lifesaving intervention or contributed to death. |
|--|---|
| Adverse Reaction (AR) | An untoward and unintended response resulting from an intervention related to the use of an investigational product. |
| Serious Adverse Event (SAE) | A serious adverse event is any untoward medical occurrence that: results in death is life-threatening requires inpatient hospitalisation or prolongation of existing hospitalisation results in persistent or significant disability/incapacity Other 'important medical events' may also be considered a serious adverse event when, based upon appropriate medical judgement, the event may jeopardise the participant and may require medical or surgical intervention to prevent one of the outcomes listed above. NOTE: The term "life-threatening" in the definition of "serious" refers to an event in which the participant was at risk of death at the time of the event; it does not refer to an event which hypothetically might have caused death if it were more severe. |
| Serious Adverse Reaction (SAR) | An adverse event that is both serious and, in the opinion of the reporting Investigator, believed with reasonable probability to be due to one of the trial methodologies or treatments, based on the information provided. |
| Suspected Unexpected Serious Adverse Reaction (SUSAR) | Any events suspected to be caused by the investigational product, but which are not consistent with information about the investigational product. |

11.1.2 Safety Reporting Window

Participants will be monitored for adverse events while they are enrolled on the study, and given contact details (telephone number and email address) to report any adverse events that may occur. Once their involvement in the study has ended, they will have an additional 6 weeks in which to contact the Investigators with details of any adverse events that become apparent after they have been unenrolled. Therefore, the Safety Reporting Window will be from enrolment until 12 weeks after disenrollment.

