11.1.4 Procedure for Reporting Adverse Events

All AEs occurring during the safety window for the trial as defined above that are observed by the Investigator or reported by the participant, will be recorded during visits on the participants electronic

health record as source data and recorded on the CRF for the purposes of the study, whether or not attributed to the Salurate device.

The following information will be recorded on the CRF: description, date of onset and end date, severity, assessment of relatedness to investigational product, other suspect drug or device and action taken. Follow-up information should be provided as necessary until the AE has resolved or stabilised.

The severity of events will be assessed on the following scale: 1 = mild, 2 = moderate, 3 = severe.

Non-serious AEs considered related to the study intervention as judged by the Principal or Chief Investigator or the Sponsor will be followed up until resolution, or the event is considered stable.

It will be left to the Investigator's clinical judgment to decide whether an AE is of sufficient severity to require the participant's removal from treatment. A participant may also voluntarily withdraw from treatment due to what they perceive as an intolerable AE. If either of these occurs, the participant will be thanked for their involvement and followed up by telephone until the AE is resolved or considered stable. All withdrawals must be recorded using document *HR-P-62 - Early Withdrawal Form*.

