23 POST-STUDY CARE

The Salurate Study is non-interventional and will cease with the end of pregnancy. Throughout the study and after, participants will receive standard medical care.

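### The 12-week safety window does not follow from the 6 weeks stated beside it, and the adverse event definition leaves almost no room for the non-serious events the protocol sets out to follow

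*Protocol*

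**What the plan says.** **Window.** Section 11.1.2 monitors women for adverse events while they are enrolled. It continues: "Once their involvement in the study has ended, they will have an additional 6 weeks in which to contact the Investigators", and this is for "adverse events that become apparent after they have been unenrolled". The concluding sentence is "Therefore, the Safety Reporting Window will be from enrolment until 12 weeks after disenrollment".

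**Neighbouring periods.** Section 10.6 collects outcome diagnoses "for a period of 6 weeks following the conclusion of pregnancy". Section 23 states: "The Salurate Study is non-interventional and will cease with the end of pregnancy".

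**Definitions.** Section 11.1.1 describes an AE as an "event in which care resulted in an undesirable clinical outcome". It excludes outcomes of underlying disease and requires one of four consequences: longer hospital care, permanent harm, a lifesaving intervention, or a contribution to death. The same table defines a serious adverse event (SAE) from a wider starting point, any untoward medical occurrence. It also defines an adverse reaction (AR) as an unintended response to the investigational product, with no threshold of gravity.

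**Procedures.** Section 11.1.3 classes an AE as not related when the woman's clinical state or another therapy probably produced it. Section 11.1.4 puts all AEs in the safety window on the CRF, whether or not they are attributed to the device. It adds: "The severity of events will be assessed on the following scale: 1 = mild, 2 = moderate, 3 = severe". It also sets follow-up for related AEs that are not serious. Section 15 says that AE and SAE details will be listed.

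**The concern.** The window and the AE definition together decide which events a site writes on the CRF. If the window sentence does not follow from its premise, and its starting date is undefined, a site has to guess when recording stops. If the definition admits almost only serious events, then the follow-up of non-serious AEs in Section 11.1.4 has almost nothing to apply to. A minor event caused by the sampling kit would then go unrecorded by a site that follows the protocol to the letter. At stake is the completeness of the AE listings for a device whose safety record this study will help to form.

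**Working it through.** No sample-size formula applies. The check is arithmetic on the window and a comparison of the definitions with the procedures.

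**1. The window from its own premise.** Input: 6 weeks after involvement ends (Section 11.1.2).
- Window end = 0 + 6 = 6 weeks after disenrolment.
- Stated: 12 weeks. Gap: 12 - 6 = 6 weeks, a factor of two. The stated figure is not reproduced.

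**2. Can 12 be reached another way?** Add the 6 weeks of outcome collection (Section 10.6) to the 6 weeks of contact: 6 + 6 = 12 weeks after the end of pregnancy. This works only if disenrolment means the end of pregnancy while the end of involvement, and being unenrolled, mean a point 6 weeks later. Section 11.1.2 uses the three terms as one point and does not mention outcome collection.

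**3. What the missing anchor does.** For a woman who completes the study, counting weeks from the end of pregnancy:

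| Disenrolment taken as | 6-week statement | 12-week statement |
|---|---|---|
| End of pregnancy | 0 + 6 = 6 | 0 + 12 = 12 |
| End of outcome collection | 6 + 6 = 12 | 6 + 12 = 18 |

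Even if only the 12-week sentence is applied, the end date moves between 12 and 18 weeks.

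**4. Ceiling on the time in dispute.** 4,000 x 6/52 = 461.5, about 462 woman-years, if every one of the 4,000 women reaches this period.

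**5. AE consequences against SAE criteria (Section 11.1.1).**
- Longer hospital care: matches prolonged hospitalisation.
- Permanent harm: close to persistent or significant disability.
- Lifesaving intervention: close to life-threatening.
- Contribution to death: close to resulting in death.

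The match is near, not exact; a trivial permanent harm might escape the SAE criteria. In practice almost every event that meets the AE definition is also serious. In cause the AE definition is the narrower of the two, since it needs an outcome of care and excludes underlying disease, while the SAE definition has no such limit.

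**6. Against the procedures.**
- Section 11.1.4 follows up non-serious AEs, a class that step 5 leaves almost empty.
- Section 11.1.3 has AEs produced by the woman's clinical state. The definition requires a cause in care and excludes underlying disease, so such an event largely cannot be an AE. The other limb, other therapies, does fit.
- The serious adverse reaction entry in Section 11.1.1 speaks of an adverse event that is also serious, which presumes that some are not.

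**7. Path to the data.** Section 11.1.4 records AEs, not ARs. A minor reaction to the kit meets the AR definition but not the AE definition, so no recording rule reaches it. Serious events are still reported under Section 11.1.5.

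**The case against.** The strongest replies are these.

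- **One operative window is stated.** Section 11.1.2 names the Safety Reporting Window, sets 12 weeks, and Section 11.1.4 refers back to it. This stands in part. A reader might infer that no end date can be programmed, but the text does give a nominal one. What remains is that its reasoning does not support it and its anchor is undefined.
- **The other periods serve other purposes.** A reader might infer that Sections 10.6 and 23 contradict the safety window and must be made equal to it. They need not be: one governs outcome collection, the other is about care after the study. Forcing 10.6 to 12 weeks would double primary-outcome collection, which is a design change.
- **Severity is not seriousness.** A reader might take the mild grade as a direct contradiction of the definition. It is not, because the two scales differ. Nor does recording events regardless of attribution to the device conflict, since the definition refers to care and not to the device. The evidence that holds is the provision for non-serious AEs and Section 11.1.3.
- **The AR definition covers minor device effects.** It does, but Section 11.1.4 does not use it.
- **Little depends on it.** A reader might infer that AE rates will not be comparable between sites. Section 15 plans listings, not rates or site comparisons. Section 7.4 states that saliva collection has no known side effects.

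**Conclusion.** Both inconsistencies are in the text. The premise of Section 11.1.2 gives 6 weeks against the 12 stated, and the undefined date of disenrolment can shift the end by another 6 weeks. The AE definition nearly duplicates the SAE criteria, is partly narrower than the SAE definition, and does not fit Sections 11.1.3 and 11.1.4.

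The consequence is limited to safety data: read literally, the protocol keeps non-serious events, device-related ones included, off the CRF and out of the AE listings. The number lost cannot be estimated, because the protocol gives no expected AE frequency. The 462 woman-years is a ceiling: it assumes that all 4,000 women are followed, and the period is one in which women may make contact, not one of scheduled visits. Sample size, precision and the primary analysis are unaffected. That sites would in fact apply different windows is a risk, not something the text dictates. The point should be corrected, but it does not threaten the study's main result.

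**What to change.** 1. In Section 11.1.2, reconcile the 6-week and 12-week statements into one window, and define disenrolment as a dated event, both for women who complete the study and for those who withdraw. The sponsor and investigator decide which window applies. If 6 plus 6 weeks was intended, say so and name both starting points.
2. In Section 11.1.1, reword the AE definition so that it includes non-serious events regardless of cause and agrees with Sections 11.1.3 and 11.1.4. Keep the grave consequences as criteria for the SAE definition only.
3. Leave the outcome-collection period in Section 10.6 and the statement in Section 23 as they are; neither has to match the safety window.

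The cost is a wording amendment through the route in Section 22, plus some added CRF entries for non-serious events. The participant information sheet is not at hand, so it should be checked for the period that women are told; whether it needs changing cannot be said from the protocol.
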